## 9 Research Methods

## 9.1 Study Design

### 9.1.1 Design Overview

[figure not shown]
This study is a prospective, international, single-arm, observational real-world study in patients with advanced RCC. This multicenter study will be conducted at approximately 30 centers in various European countries. A total of approximately 100 patients, who are currently receiving Avelumab (800 mg intravenously every 2 weeks) plus Axitinib (5 mg orally twice per day) in accordance with the terms of the marketing authorization for the first-line therapy, will be selected. Patient assignment to Avelumab plus Axitinib therapy should be decided in advance by the treating physician and fall within current clinical practice prior to study enrollment. There will not be any study-specific interventions in this study. The study size is further described in [Section 9.5](#).

The index date (baseline visit) is defined as the first administration date, after informed consent, of Avelumab plus Axitinib therapy to patients with advanced RCC. Patients will be recruited over a period of approximately 24 months and will be followed up for 24 months from the index date, irrespective of whether they continue or discontinue the study treatment. There will be a safety follow-up at 90 days post discontinuation of Avelumab plus Axitinib therapy.

Study visits will be scheduled according to routine clinical practice in terms of visit frequency and types of performed treatments and assessments. Due to the observational nature of this study, planned assessments will be recorded as part of routine clinical practice, in line with the approved SmPC and as clinically indicated.

Figure 1 below provides a schematic overview of the study design.

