### **9.7.1 Analysis Sets**

All eligible patients, who provided written informed consent and received 1 or 2 cycles of Avelumab plus Axitinib treatment as a first-line therapy prior to informed consent, will be included in the analysis. All planned analyses will be descriptive, no formal statistical comparisons will be performed.

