### **9.7.2 Derived and Transformed Data**

Primary and secondary effectiveness outcomes will be derived as per definition reported in [Section 9.1.2](#).

For OS, PFS, PFS2 and DoR, the percentage of patients alive at the time of outcome assessment (12 or 24 months) will be calculated as per the Kaplan-Meier approach.

For PFS, PFS2 and DoR, a patient progressing after stopping current treatment and starting a new therapy will be censored at the latest tumor assessment showing no progression before changing therapy.

For safety, time to onset of AE will be calculated as difference in days between start date of AE and the index date +1, while duration of AE (applicable for resolved AEs only) will be calculated as difference in days between end date of AE and start date of AE +1.

Time to Avelumab plus Axitinib discontinuation will be derived as difference in days between last dose of Avelumab plus Axitinib and the index date +1 and time to second-line therapy after study treatment discontinuation will be calculated as difference in days between start date of second-line treatment and last dose of Avelumab plus Axitinib +1.

As per NCCN-FACT Fksi-19 scoring guidelines (version 2), the total HRQoL score (range 0-76) will be calculated as sum of single items scores multiplied by 19 and divided by the number of items completed. NCCN-FACT Fksi-19 will also cover 4 subscales: DRS-P (items from 1 to 11, range 0-48), DRS-E (item 12, range 0-4), TSE (items from 13 to 15, range 0-12) and FWB (items from 16 to 19, range 0-12). The higher the subscores or the total score, the better the HRQoL. The subscales will be evaluable, if at least 50% of respective items will be answered and will be calculated as sum of items included in the subscale, multiplied by the item included in the subscale, and divided by the item answered in the subscale. The Fksi-19 questionnaire as a whole will be evaluable, if all subscales will be evaluable and at least 80% of all items will be answered. Score of items 11 (C6), 12 (GF5), and from 16 to 19 (GF1, GF3 and GF7) will be reversed before calculating total and subscale scores.

Every effort will be made to capture all available data by:

- Ensuring that primary variables of interest are those that are routinely collected as part of routine clinical practice and are available via medical charts, physician, and/or patient/caregiver reporting, as appropriate

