Anti-cancer therapy after end of study treatment will be summarized according to the respective eCRF page. Treatments will be categorized by means of coding and medical review. The same approach as for CMs will be applied based on ATC level 2 and PT.

Number and percentage of participants with any anti-cancer post study treatment and by type [(immunotherapy, targeted therapy, chemotherapy, radiotherapy, other)] will be presented.

Number and percentage of participants treated with targeted therapies, monoclonal antibodies and other protein kinase inhibitors as post study treatment (based upon ATC coding) will be presented including PT separately for:

- Anti-vascular endothelial growth factor (VEGFR, ATC code L01EK)
- Tyrosine kinase inhibitors (TKIs, ATC code L01EB)
- Mammalian target of rapamycin (mTOR, ATC code L01EG)
- Monoclonal antibodies (ATC code L01EX)
- Other protein kinase inhibitors (ATC code L01XC).

Summary statistics will be created for intent of therapy (Neo-Adjuvant / Adjuvant / Metastatic or Locally advanced), line number, duration, and best response across all post study treatments. For

participants who received more than one anti-cancer therapy after treatment discontinuation, the BOR among all anti-cancer therapies will be summarized.

13**Study Treatment: Compliance and Exposure**

The following analyses will be performed based on the analysis set for Avelumab and Axitinib by visit.

All dosing calculations and summaries will be based on “Avelumab Administration” and “Axitinib Administration” eCRFs pages.

No imputation of missing start dates of study treatments will be done.

In case the last date of study drugs is incomplete the date of last study drugs administration will be taken from the EOT page. A dose is regarded to be administered if the actual dose received is > 0.

Exposure duration and cumulative dose for each treatment of the combination will be summarized after being derived in days respectively as difference between last treatment date–index date +1, for Axitinib (days unit) and (last treatment date – index date +14) for Avelumab and the sum of the actual doses of study drugs received overall. For Avelumab, duration will also be expressed in terms of cycles and derived as (last treatment date – index date +14)/14 considering each cycle duration of 2 weeks.

The summary of treatment exposure will include the following information:

- Exposure duration (days/cycles)
- Cumulative dose (milligrams)

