15.2 Deaths, Other Serious Adverse Events, and Other Significant Adverse Events

15.2.1 Deaths

The following summaries for the deaths will be reported in a table:

- Number and percentages of deaths
- Number and percentages of deaths due to COVID-19 (identified based on specification collected when reason for death corresponds to “Event unrelated to study treatment”)
- Number and percentages for each primary reason of death (percentage calculated using the number of deaths as denominator):
 - Progressive disease and/or disease related condition
 - Event unrelated to study treatment
 - Event related to Avelumab
 - Event related to Axitinib
 - Unknown.

A listing with the following columns will be presented:

- Patient number
- Age (yrs.)/ Sex/ Weight (kilograms)
- First dose date, last dose date, dose in milligram or dose not administered for Avelumab and Axitinib
- Date of death
- Primary cause of death
- If event unrelated to study treatment, specify
- Fatal AE
- Period

- irAE or IRR flag

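### Exposure duration, avelumab cycles and time to discontinuation start at the index date, so therapy duration omits the 1 or 2 cycles every patient received before consent (nominally 14 or 28 days)

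*SAP*

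**What the plan says.** Protocol 9.1.1 fixes time zero: "The index date (baseline visit) is defined as the first administration date, after informed consent, of Avelumab plus Axitinib therapy". Protocol 9.7.1 and SAP 8.1 restrict the Analysis Set to eligible patients who "received 1 or 2 cycles of Avelumab plus Axitinib treatment as a first-line therapy prior to informed consent". The index dose is therefore nominally the start of cycle 2 or cycle 3.

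SAP Section 13 derives axitinib exposure as "last treatment date–index date +1, for Axitinib (days unit"), and avelumab exposure in days from the same origin with +14 in place of +1. Avelumab cycles are "derived as (last treatment date – index date +14)/14 considering each cycle duration of 2 weeks". Cumulative dose is "the sum of the actual doses of study drugs received overall". Actual dose intensity is that sum divided by exposure duration. Relative dose intensity divides actual intensity by planned cumulative dose over exposure duration.

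Protocol 9.7.2 defines time to discontinuation as the "difference in days between last dose of Avelumab plus Axitinib and the index date +1".

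SAP Section 5 lists, as a secondary endpoint, the duration of combination therapy among patients who stopped because of an AE of Grade 3 or higher. SAP 15.1.1 reports it through the exposure duration and cumulative dose of those patients.

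**The concern.** The endpoint is named as duration of therapy, but the formula measures time on therapy after enrolment. Nothing in either document adds the earlier cycles back or warns that they are missing, and Protocol 9.9 does not list this among the limitations. SAP 9.9 treats the two dates as one: it uses the index date as the start of study treatment when completing partial AE dates, and as the treatment start date available for all patients.

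The loss is a fixed number of days, so it weighs most on patients who stop early. Patients who stop for a severe AE may well be among them, and they are the group the endpoint describes. A reader who compares the reported duration, or time to discontinuation, with a study that counts from first dose would see shorter treatment here for a reason unrelated to tolerability.

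**Working it through.** The documents state no exposure result, so there is no figure to reproduce. The check applies the SAP formulas to a patient dosed on schedule.

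**Inputs**
- Cycle length: 14 days (SAP 13).
- Cycles before the index date: k = 1 or 2 (Protocol 9.7.1, SAP 8.1).
- Avelumab as described in Protocol 9.1.1: 800 mg every 2 weeks (used for illustration only).
- N: total avelumab infusions, including those before the index date.

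**Step 1: does the cycle formula count correctly from the index date?** With m infusions from the index date onward, last − index = 14(m − 1). Then (14(m − 1) + 14)/14 = m. The formula is right for post-index cycles. Only its origin is in question.

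**Step 2: the shortfall.** On schedule, the index date falls 14k days after first dose.
- Avelumab from first dose: 14(N − 1) + 14 = 14N days.
- Avelumab by SAP 13: 14(N − 1) − 14k + 14 = 14(N − k) days.
- Difference: 14k, which is 14 days (1 cycle) or 28 days (2 cycles).

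Axitinib exposure and time to discontinuation use +1 instead of +14. The constant cancels, so their shortfall is also 14 or 28 days.

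**Step 3: share of true duration**, 14k/(7w) for w weeks on drug:

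| True duration | k = 1 | k = 2 |
|---|---|---|
| 8 weeks (56 days) | 14/56 = 25.0% | 28/56 = 50.0% |
| 12 weeks (84 days) | 14/84 = 16.7% | 28/84 = 33.3% |
| 24 weeks (168 days) | 14/168 = 8.3% | 28/168 = 16.7% |
| 52 weeks (364 days) | 14/364 = 3.8% | 28/364 = 7.7% |

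For scale, Protocol Section 7 gives an updated median PFS of 13.3 months in the pivotal trial (overall population). If that is taken as a treatment duration, which is an assumption, it is 13.3 × 30.4375 = 404.8 days and the shortfall is 3.5% or 6.9%. Over 24 months (730.5 days) it is 1.9% or 3.8%.

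**Step 4: actual dose intensity.** Two cases are possible, because the documents do not say whether pre-index doses enter the sum.
- Only doses from the index date are summed: 800(N − k)/(N − k) = 800 mg per cycle. No distortion.
- Pre-index doses are included: 800N/(N − k) mg per cycle. For k = 1 or 2, N = 4 gives 1067 or 1600, N = 12 gives 873 or 960, and N = 29 gives 829 or 859.

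**Step 5: relative dose intensity.** With actual dose A, planned dose P and exposure duration D, the SAP formula is 100 × (A/D)/(P/D) = 100 × A/P. Duration cancels. The result is inflated by N/(N − k) only if A includes pre-index doses and P starts at the index date.

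**The case against.** The index date is the declared and consistent origin of the study. OS and PFS run from it, and SAP 9.3 makes it Day 1. The analyses are descriptive, the offset is bounded by eligibility, and it becomes small for patients treated for a year or more. The documents give no distribution of treatment duration, so the 25–50% figure describes a short-treated patient and not the cohort. All of this stands, and it limits the size of the point. It does not make post-enrolment time the same thing as duration of therapy.

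Several stronger readings are tempting, and the documents do not support them:

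- *Dose intensity is inflated.* A reader might infer that relative dose intensity at full dosing would read 110–120% with 10 post-index cycles, or 125–150% with 4. By step 5, dividing by post-index time is not enough. The planned dose must also start at the index date while the actual dose starts earlier. The SAP describes both sums as overall, so matching windows are the more natural reading. Table 1 of the Protocol schedules therapy data from W0, which suggests that recorded doses begin at the index date. The deaths listing in SAP 15.2.1 ("First dose date, last dose date, dose in milligram or dose not administered for Avelumab and Axitinib") does not say which first dose it means and does not show that earlier doses are captured.
- *AE onset times are wrong.* Protocol 9.1.2.2 expressly defines onset from the index date, and Protocol 11.4 starts AE recording only at consent. Onset from first dose would span a period in which no AEs are recorded.
- *Every duration is short.* AE duration, DoR and time to second-line therapy do not use the index date.
- *The primary result is affected.* The exposure formula does not enter the 12-month OS rate.

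**Conclusion.** The point holds for exposure duration of both drugs, avelumab cycles and time to discontinuation, and so for the secondary endpoint on therapy duration in patients stopping for AEs of Grade 3 or higher. As written, these are short by a nominal 14 or 28 days (1 or 2 cycles), with the relative loss shown in step 3. The size assumes that the pre-index cycles were given on the 2-week schedule; a delayed early cycle makes the shortfall larger. The documents give no actual interval between first dose and index date.

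Dose intensity is a conditional concern. Actual intensity is inflated if pre-index doses are summed while duration runs from the index date. Relative intensity is inflated only if planned dose also starts at the index date. The SAP should settle both windows. AE onset needs a clear label but no new definition.

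**What to change.** 1. Abstract the date of the first avelumab plus axitinib dose. It is already needed to verify inclusion criterion 5 and exclusion criterion 2 in Protocol 9.2.1.
2. In SAP 13 and Protocol 9.7.2, derive therapy duration, avelumab cycles and time to discontinuation from that date. Use it for the Grade 3 or higher discontinuation endpoint.
3. Keep the index-based values as a second set, labelled on-study exposure.
4. State one window for actual dose, planned dose and exposure duration, and say whether pre-index doses are included.
5. Keep AE onset as the Protocol defines it, labelled as time from index date and not time since first exposure. State in the SAP 15.2.1 listing which first dose is meant.

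The cost is one chart date for about 100 patients, plus the pre-index doses if cumulative dose is to cover them, and revised SAP and Protocol wording. Treatment, visits and the primary analysis do not change.

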14.1 Primary Endpoint: Overall Survival Rate at 12 Months

14.1.1 Primary Objective: Derivation and Analysis of the Primary Endpoint: Overall Survival Rate at 12 Months

Endpoint Derivation

OS Rate at 12 months	OS rate is defined as the percentage of patients who are alive at 12 months after the index date. OS rate will be presented along with 95% CI. Percentage of patients alive at the time of outcome assessment (12 months) will be calculated as per the KM approach.
-----------------------------	--

[REDACTED]
[REDACTED]
[REDACTED]
[REDACTED]
[REDACTED]
(collected in “[REDACTED]” eCRF page)

14.1.3 Supplementary Analyses of the Primary Endpoint Overall Survival Rate at 12 Months

Not applicable.

14.1.4 Subgroup Analyses of the Primary Endpoint Overall Survival Rate at 12 Months

The subgroup analyses will be performed on the primary endpoint based on the analysis set for all subgroup levels defined in [Section 8.2](#) “Subgroup definition and parametrization”. All the subgroup analyses are exploratory and will be performed unstratified.

No adjustment for multiplicity will be performed. In the case of a low number of participants within a category of the analysis set, the categories will be pooled when meaningful (see [Section 8.2](#)).

14.2 Further Endpoints

Endpoint Derivations

OS Rate at 24 months	OS rate is defined as the percentage of patients who are alive at 24 months after the index date. OS rate will be presented along with 95% CI.
-----------------------------	--

	Percentage of patients alive at the time of outcome assessment (24 months) will be calculated as per the KM approach.
OS	
OS is defined as the time from index date to the date of death due to any cause. OS for participants without death prior to cut-off will be censored at date of last contact. OS in months is calculated as follows:
 $\text{OS (months)} = [\text{date of death or censoring} - \text{index date} + 1] / 30.4375$ 
Note: If death events occurring after cut-off are to be taken into account, the table below may be used for OS. Nevertheless, this will not be the standard process.
 
OS will be estimated by the KM method. The percentage of censored patients will also be reported. Median event time will be reported, along with 25th and 75th percentiles. Percentage of patients experiencing event or being event-free at applicable timepoints will also be reported along with the corresponding two-sided 95% CIs.
 
Analyses of overall survival time

PFS	
PFS time is defined as the time from index date to the date of the first documentation of objective PD or death due to any cause, whichever occurs first. The tumor response will be determined according to Response Evaluation Criteria in Solid Tumours (RECIST) v 1.1 and assessed by the investigator.
 $\text{PFS time (in months)} = (\text{Date of PD or death} - \text{index date} + 1) / 30.4375 \text{ (months)}$

PFS data will be censored on the date of the last adequate tumor assessment for participants who do not have an event (PD or death) or start a subsequent anti-cancer therapy prior to an event. Participants who do not have any post-baseline tumor assessments will be censored on the start date.

The last adequate tumor assessment is defined as the last tumor assessment result that is not “NE” or “NA”.

The censoring and event date options to be considered for the PFS analysis is presented in below table.

PFS will be estimated by the KM method. The percentage of censored patients will also be reported. Median event time will be reported, along with 25th and 75th percentiles. Percentage of patients experiencing event or being event-free at applicable timepoints will also be reported along with the corresponding two-sided 95% CIs.

Table 4 Outcome and event dates for PFS

Scenario	Date of event/censoring	Outcome
PD or death before subsequent anti-cancer therapy	Date of PD or death	Event
PD or death after subsequent anti-cancer therapy	Date of last adequate tumor assessment ^a documenting no PD before subsequent anti-cancer therapy is given	Censored
No PD/Death	Date of last adequate tumor assessment ^a documenting no PD before subsequent anti-cancer therapy is given	Censored
Treatment discontinuation due to 'Disease progression' without documented progression	Not applicable	Information is ignored. Outcome is derived based on documented progression only.
Study end for consent withdrawn without PD or death	Date of last adequate tumor assessment ^a documenting no PD before subsequent anti-cancer therapy is given	Censored

	Study end for lost to follow-up without PD or death	Date of last adequate tumor assessment ^a documenting no PD before subsequent anti-cancer therapy is given	Censored
^a If there are no adequate post-baseline assessments prior to the PD or death, then the time without adequate assessment should be measured from the index date; if the criteria were met the censoring will be on the index date.			
PFS2	
PFS2 time is defined as the time from the index date to the date of disease progression on second-line treatment or death from any cause, whichever comes first. The tumor response will be determined according to RECIST v 1.1 and assessed by the investigator.
 
PFS2 time (in months) = (Date of PD or death after second-line treatment start – index date + 1) / 30.4375 (months).
 
PFS2 data will be censored on the date of the last adequate tumor assessment for participants who do not have an event (PD or death) or start a further subsequent anti-cancer therapy prior to an event. Participants who do not have any post-baseline tumor assessments will be censored on the start date.
 
The last adequate tumor assessment is defined as the last tumor assessment result that is not “NE” or “NA”.
 
The censoring and event date options to be considered for the PFS2 analysis are presented in below table.
 
PFS2 will be estimated by the KM method. The percentage of censored patients will also be reported. Median event time will be reported, along with 25th and 75th percentiles. Percentage of patients experiencing event or being event-free at applicable timepoints will also be reported along with the corresponding two-sided 95% CIs.
		

Table 5 Outcome and event dates for PFS2
			
Scenario	Date of event/censoring	Outcome	
PD or death after further subsequent anti-cancer therapy	Date of PD or death	Event	
PD before further subsequent anti-cancer therapy	Date of last adequate tumor assessment ^a documenting no PD after further subsequent anti-cancer therapy is given	Censored	

	No PD/Death	Date of last adequate tumor assessment ^a documenting no PD after further subsequent anti-cancer therapy is given	Censored		
	Treatment discontinuation due to 'Disease progression' without documented progression	Not applicable	Information is ignored. Outcome is derived based on documented progression only.		
	Study end for consent withdrawn without PD or death	Date of last adequate tumor assessment ^a documenting no PD after subsequent anti-cancer therapy is given	Censored		
	Study end for lost to follow-up without PD or death	Date of last adequate tumor assessment ^a documenting no PD after subsequent anti-cancer therapy is given	Censored		
^a If there are no adequate post-baseline assessments prior to the PD or death, then the time without adequate assessment should be measured from the index date; if the criteria were met the censoring will be on the index date.					
ORR	The ORR will be calculated along with the two-sided 95% CI using the Clopper-Pearson method. In addition, the frequency (number and percentage) of participants with BOR of CR, PR, SD, PD and NE will be tabulated. Investigator response will be used to determine the BOR up to 24 months derived as per documented BOR considering the order CR>PR>SD>PD. [REDACTED]				
DCR	DCR is defined as proportion of participants with BOR of CR, PR, SD and will be calculated along with the two-sided 95% CI using the Clopper-Pearson method. Investigator response will be used to determine the BOR up to 24 months derived as per documented BOR considering the order CR>PR>SD>PD. [REDACTED]				
DoR	DoR is defined, for participants with BOR CR or PR only, as the time interval from the first CR or PR criteria met, whichever was reported earlier, until the date of documented overall disease progression. BOR will be derived as documented BOR. [REDACTED] If a participant has not had the event, DoR is censored at the date of last adequate tumor assessment.				

	
DoR (months) = [date of event or censoring–date of first CR or PR +1]/30.4375
 
DoR will be estimated by the KM method. The percentage of censored patients will also be reported. Median event time will be reported, along with 25th and 75th percentiles. Percentage of patients experiencing event or being event-free at applicable timepoints will also be reported along with the corresponding two-sided 95% CIs.

Table 6 **Outcome and event dates for DoR**

Scenario	Date of event/censoring	Outcome
PD before subsequent anti-cancer therapy	Date of PD	Event
PD after subsequent anti-cancer therapy	Date of last adequate tumor assessment ^a documenting no PD before subsequent anti-cancer therapy is given	Censored
No PD/Death	Date of last adequate tumor assessment ^a documenting no PD/Death before subsequent anti-cancer therapy is given	Censored
Treatment discontinuation due to 'Disease progression' without documented progression	Not applicable	Information is ignored. Outcome is derived based on documented progression only.
Study end for consent withdrawn without PD	Date of last adequate tumor assessment ^a documenting no PD before subsequent anti-cancer therapy is given	Censored
Study end for lost to follow-up without PD	Date of last adequate tumor assessment ^a documenting no PD before subsequent anti-cancer therapy is given	Censored

^a If there are no adequate post-baseline assessments prior to the PD, then the time without adequate assessment should be measured from the index date; if the criteria were met the censoring will be on the index date.

T2LT

T2LT is defined as the time from the last dose of Avelumab plus Axitinib to the start date of second-line treatment for RCC.

	T2LT time (in months) = (Second-line treatment start date – last dose of Avelumab plus Axitinib + 1)/ 30.4375 (months)
--	--

	T2LT will be summarized by descriptive statistics for continuous variables.
--	---

The subgroup analyses will be performed on selected secondary endpoints (OS, DCR, PFS, and PFS2) based on the analysis set for all subgroup levels defined in [Section 8.2](#) “Subgroup definition and parametrization”. All the subgroup analyses are exploratory and will be performed unstratified.

No adjustment for multiplicity will be performed. In the case of a low number of participants within a category of the analysis set, the categories will be pooled when meaningful (see [Section 8.2](#)).

15 Safety Analyses

This section includes specifications for summarizing safety endpoints that are common across clinical studies such as AEs, laboratory tests and vital signs.

Safety analyses will be done on the analysis set.

